4.3 Exclusion Criteria

Patients who exhibit any of the following characteristics will be excluded from the study.

1. Diagnosis of type 1 diabetes mellitus or maturity-onset/diabetes of the young (MODY)
2. Hemoglobinopathy that affects HbA1c measurement
3. Frequent symptomatic hypoglycemia (greater than one episode per week on average)
4. Genitourinary tract infection within 6 weeks of screening or history of \geq 3 genitourinary infections requiring treatment within the last 6 months
5. Cancer, active or in remission for $<$ 3 years (Non-melanoma skin cancer or basal cell carcinoma or carcinoma *in situ* of the cervix will not be grounds for exclusion)
6. History of alcohol or illicit drug abuse in the past 2 years
7. Evidence of abnormal liver function tests (total bilirubin or alkaline phosphatase $>$ 1.5 x upper limit of normal (ULN) with the exception of isolated Gilbert's syndrome); or alanine aminotransferase (ALT) or aspartate aminotransferase (AST) $>$ 2.5 x ULN
8. History of MI, stroke or hospitalization for heart failure in the prior 3 months
9. Evidence of NYHA class IV heart failure at screening or randomization
10. Presently scheduled for percutaneous coronary intervention, coronary artery bypass grafting or any surgical procedure
11. Previous treatment with bexagliflozin or EGT0001474

12. Currently or within 3 months of taking any SGLT2 inhibitors ([Appendix 3](#))
13. Any condition, disease, disorder, or clinically relevant laboratory abnormality that, in the opinion of the PI, would jeopardize the subject's appropriate participation in this study or obscure the effects of treatment
14. Prior renal transplantation or evidence of nephrotic syndrome, defined as a urine albumin: creatinine ratio (UACR) > 2000 mg/g, at screening
15. Implantation of a cardiac resynchronization therapy device within 3 months prior to screening or intent to implant a cardiac resynchronization therapy (CRT) within 6 months following screening
16. Diagnosis of peripartum or chemotherapy-induced cardiomyopathy within 12 months prior to screening
17. Symptomatic bradycardia or second or third degree atrioventricular block without a pacemaker
18. eGFR, as calculated by the modification of diet in renal disease study equation (MDRD), < 45 mL/min/1.73 m² or requiring dialysis
19. Pregnant or nursing
20. Currently participating in another interventional trial.

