6.10.9 Hepatotoxicity

If plasma AST and/or ALT concentrations $> 3 \times$ ULN are detected, the investigator will record in the source documents the date corresponding to the date of the laboratory abnormality; the type, frequency, and dose of any concurrent medications or supplements taken by the subject within the 14 days of the detected abnormality; and any symptoms or change in physical exam that have occurred since the prior assessment. The investigator should perform additional laboratory and imaging tests to attempt to establish the cause of the AST and ALT elevations, including ruling out any potential contribution from bone or muscle etiologies.

Any clinically significant increase in hepatic enzymes and specifically any ALT or AST $> 3 \times$ ULN requires immediate repeat test within 48 to 72 h to confirm the hepatic enzyme elevation and should be repeated based on the clinical situation at least every 96 h (4 days) until ALT and AST return to $< 2.5 \times$ ULN. Study medication should be stopped and the event should be reported as a laboratory AE within the CRF if the enzyme elevation is confirmed or worsening.

Hepatotoxicity will be diagnosed and entered as an AE should any of the following occur:

- ALT or AST $> 8 \times$ ULN;
- ALT or AST $> 3 \times$ ULN and total bilirubin $> 2 \times$ ULN or INR > 1.5 (INR will not be measured as a routine laboratory but should be assessed when needed for medical decision making in the appropriate clinical scenario).
- ALT or AST $> 3 \times$ ULN with the appearance of fatigue, nausea, vomiting, right upper quadrant pain or tenderness, fever, rash, and/or eosinophilia ($> 5\%$).

In the event of hepatotoxicity, investigational product should be permanently discontinued. The investigator is encouraged to consult with the Medical Monitor regarding diagnostic evaluation for the hepatic enzyme elevations. Consultation with a hepatologist may also be appropriate in some circumstances.

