Descriptive statistics will be provided for clinical laboratory data, vital signs data, and ECG interval data, presented as both actual values and changes from baseline relative to each study visit. For each continuous laboratory parameter, results will be categorized as low, normal or high based on the laboratory normal ranges. Frequencies and percentages will be presented for subjects who had a shift to low and for patients who had a shift to high from baseline to any post-dosing assessment. Baseline values for all safety analyses will be defined as the last observation prior to dosing. All out-of-range and clinically significant laboratory results will be identified in patient data listings.

Abnormal physical examination findings will be tabulated by treatment and presented in a by-patient data listing.

Concomitant medications will be coded using the World Health Organization Drug Dictionary (WHO-DD). A by-subject listing of concomitant medications will include all medications taken during the study regardless of the timing for the start of the medication. All medications started prior to the administration of the investigational product will be included in the data but will be flagged as prior in the listing. Only the concomitant medication use will be summarized in terms of frequency and percentages by body system and medication name.

In addition, safety profile for subjects who were prescribed with insulin will be separately analyzed, eg, adverse events of special interest, incidences of TEAEs, laboratory abnormalities, vital signs, physical exams, and concomitant medication usages.

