6. GENERAL ASPECTS FOR STATISTICAL ANALYSIS

6.1. GENERAL METHODS

The proposed statistical methodology and analyses are in accordance with the principles outlined by the ICH E9 guidelines. All statistical analyses will be conducted using SAS statistical software version 9.3 or higher.

Tables, listings and figures (TLFs) will be produced in accordance with the principles outlined by the ICH E3 guidelines. For most summary statistics, data will be analyzed by the following treatment arms: Bexagliflozin 20 mg and Placebo. All available data from subjects who signed an informed consent will be presented in the subject listings.

Data summaries will use descriptive statistics (number of subjects [n], mean, standard deviation [SD], Q1, median, Q3, minimum and maximum) for continuous variables, and frequency and percentage of subjects for categorical and ordinal variables, unless otherwise specified.

Unless otherwise specified, all statistical tests will be one-tailed using a 0.025 level of significance. All confidence intervals (CIs) will be two-sided 95% CIs.

The analysis visit window will be assigned to data collection. One selected data point per visit will appear in summary tables and figures. Refer to section 6.4 for details. All visit assessment data will be included in shift tables and will appear in the subject listings.

No data imputation will be applied for missing values, unless otherwise specified.

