6.4. ANALYSIS VISIT WINDOWS

Table 6 shows how data will be mapped to visit number prior to selection of records for analysis. All post-baseline visits, including unscheduled and early termination visits, will be mapped.

After mapping the data to the visits, the following rules will apply unless other handling is specified for a particular analysis.

- If multiple records are available within a single visit window, the record closest to the planned assessment day will be selected for analysis.
- If 2 records are equidistant from the target day, then the later record will be selected.
- If a subject has no record in an analysis window, the data will be considered missing at that visit.

Table 6 Analysis Visit Windows

Study Day Window	Scheduled day	Scheduled Visit/Week
Day 1 - 63	Day 42	Visit 5/Week 6
Day 64 - 105	Day 84	Visit 6/Week 12
Day 106 - 147	Day 126	Visit 7/Week 18
Day 148 - 210	Day 168	Visit 8/Week 24
Day 211 - 294	Day 252	Visit 9/Week 36
Day 295 - 420	Day 336	Visit 10/Week 48
Day (xx*7-83) - minimum (xx*7+84, End of Treatment Visit date)	Day (xx*7)	Visit /Week xx, where xx is every 24 weeks.
> End of Treatment Visit date + 7	End of Treatment Visit + 28	Follow-up Visit

If there are multiple end of treatment visits, the one closest to the last dose date will be used. If multiple records are equidistant from the last dose date, the later one will be used. Analysis visit windows will be used for all lab, vital sign, and ECG data.

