laboratory reports so the sponsor, investigators, study coordinators, pharmacists, study subjects, and the adjudication committee members will remain blinded to the dosing assignment.

The baseline value for all laboratory tests will be the latest value obtained on or prior to Day 1. Change from baseline for all continuous parameters will be calculated as the post-baseline value minus the baseline value. All continuous variables will be summarized by number of subjects [n], mean, SD, Q1, median, Q3, minimum and maximum and categorical variables will be summarized by frequency and percentage.

Observed values (in SI units) and change from baseline over time will be summarized by treatment arm. Laboratory data will be classified as low, normal, or high relative to the parameter's reference range. Laboratory abnormalities for each treatment will also be summarized with shift tables for selected parameters.

For hematology, chemistry, and serum lipids, columns will be included for normal ranges and individual abnormal laboratory values will be flagged and clinical significance will be indicated.

Urine albumin/creatinine ratio (UACR) will be summarized and analyzed separately. Descriptive statistics for geometric mean, geometric coefficient of variation (gCV), median, Q1, Q3, minimum, and maximum of UACR values will be presented at screening, baseline, and all post-baseline scheduled visits for all subjects and for baseline macroalbuminuria subjects ($>300 \text{ mg g}^{-1}$). UACR data is left-skewed and will be natural log transformed first. Change in log transformed UACR from baseline to week 24 will be analyzed by ANCOVA model. The fixed effect will include region, baseline HbA_{1c} level as continuous variable, region, baseline eGFR categories (<60 or $\geq 60 \text{ mL min}^{-1} \text{ per } 1.73 \text{ m}^2$), baseline BMI ($<$ or $\geq 25 \text{ kg m}^{-2}$), history of heart failure (yes or no), insulin use or not, and treatment. The log transformed baseline values will be used as covariate. Analysis will be repeated for baseline macroalbuminuria subjects. LS means for each treatment will be estimated at week 24. The adjusted geometric mean ratio of relative change from baseline in UACR (the ratio of the week 24 geometric mean and baseline geometric mean) and the corresponding two sided 95% CI by treatment arm will be calculated as the antilog of the LS mean and 95% CI of log transformed values, converted to percentage.

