Biomarker evaluation is an exploratory study that will be analyzed and reported in a separate report. The biomarker results will not be included in the subject listing or summarized in the THR-1442-C-476 study report. Summary and shift table of hematology, summary of urinalysis, and analysis table of UACR will also be conducted for subjects who have been prescribed insulin or sulfonylurea to control their diabetes.

Table 8 List of Laboratory Tests

Test Name	Blood or urine Vol. (mL)	Shipment
Hematology¹	2 (blood)	Ambient
Hematocrit (Hct)	Mean corpuscular volume (MCV)	
Hemoglobin (Hgb)	Red cell distribution width (RDW)	
Mean corpuscular hemoglobin (MCH)		
Mean corpuscular hemoglobin concentration (MCHC)	Red blood cell (RBC) count	
Platelet count	White blood cell (WBC) count with differential	
Serum Chemistry and Electrolytes	5 (serum)	Ambient
Albumin (ALB)	Total protein	
Alanine aminotransferase (ALT)	Calcium (Ca)	
Aspartate aminotransferase (AST)	Magnesium	
Alkaline phosphatase (ALK)	Phosphorus	
Blood urea nitrogen (BUN)	Potassium (K)	
Glucose	Sodium (Na)	
Bicarbonate (HCO ₃)	Total bilirubin	
Creatinine	Direct bilirubin	
Chloride (Cl)	Uric acid	
Glycemic Control		Ambient
Fasting plasma glucose (FPG)	2 (plasma)	
Hemoglobin A _{1c} (HbA _{1c})	2 (blood)	
Serum Lipids^{1, 2}	6 (serum)	Ambient
Total cholesterol (TC)	Low-density lipoprotein cholesterol (LDL-C),	
High-density lipoprotein cholesterol (HDL-C)	calculated	
Triglycerides (TG)	LDL-C, direct	
Urinalysis³	10 (urine)	Ambient
Appearance	Nitrite	
Bilirubin	Occult blood	
Color	pH	
Glucose	Protein	
Ketones	Specific gravity	
Microscopic examination of sediment	Urobilinogen	
UACR	Leukocyte esterase	
Infectious Disease Testing	9 (serum)	Ambient
HBsAg	HCV	
HIV (Canada only)		
Urine pregnancy test (WOCBP)	2 (urine)	Local
Population PK Sampling	2 (plasma)	Frozen
Bexagliflozin plasma level		
Biomarker evaluation	5 (serum)	Ambient
NT-proBNP evaluation (select Group 2 subjects)	5 (serum)	Ambient

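### No by-arm table counts subjects who meet the protocol's numeric liver criteria (ALT/AST >8x ULN, or ALT/AST >3x ULN with total bilirubin >2x ULN), so the hepatotoxicity AE count has no laboratory cross-check

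*Combined protocol and SAP*

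**What the plan says.** Protocol 6.10.9 gives three routes to a hepatotoxicity event: ALT or AST >8x ULN; ALT or AST >3x ULN with total bilirubin >2x ULN or INR >1.5; and ALT or AST >3x ULN with listed symptoms or eosinophilia. Its instruction is "Hepatotoxicity will be diagnosed and entered as an AE should any of the following occur", and the product is then stopped permanently. Protocol 6.10.2 separately makes AST, ALT or bilirubin >3x ULN a laboratory AE.

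For analysis, SAP 9.4 states "Laboratory data will be classified as low, normal, or high relative to the parameter's reference range" and "Laboratory abnormalities for each treatment will also be summarized with shift tables for selected parameters". The selected parameters are not named. The one group that SAP 9.4 names for a shift table is hematology, in the insulin and sulfonylurea subsets: "Summary and shift table of hematology, summary of urinalysis, and analysis table of UACR will also be conducted". SAP 9.4 also gives descriptive statistics by arm over time, including the maximum, and flags abnormal values in listings with the normal range and clinical significance.

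Protocol 9.6.4 uses the same three classes for every continuous parameter and adds "Frequencies and percentages will be presented for subjects who had a shift to low and for patients who had a shift to high from baseline".

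Hepatotoxicity is an AE of special interest in both documents. Protocol 9.6.4 and SAP 9.3.3 identify it from MedDRA terms, and SAP 9.3.3.1 reports it by arm as number, percentage and rate per 100 patient years.

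**The concern.** The protocol sets exact enzyme and bilirubin limits and attaches permanent discontinuation to them, but the analysis text never uses those limits. A three-class laboratory scheme puts a trivial ALT rise and one above 8x ULN in the same cell. A preferred term carries neither the multiple of ULN nor the fact that enzyme and bilirubin rose together.

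At stake is whether the study report can show, by arm, how many subjects met the >8x criterion or the joint criterion, and whether the hepatotoxicity AE count agrees with the laboratory database. As written, a reader would have to work that out from listings, and the AE count would rest on investigator recognition, wording and coding without an objective comparison.

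**Working it through.** The plan states no figure to reproduce. The check compares each planned by-arm output with the two numeric criteria.

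1. **Laboratory classes (SAP 9.4, protocol 9.6.4).** There are three: low, normal, high. The protocol treats three ALT/AST bands differently: above ULN up to 3x, above 3x up to 8x, and above 8x. All three fall in one class, high. So 1.1x and 9x ULN are classed alike.

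2. **Shift to high (protocol 9.6.4).** Protocol 4.3 (the criterion beginning "Evidence of abnormal liver function tests (total bilirubin or alkaline phosphatase") excludes ALT or AST only when above 2.5x ULN, so a subject can enter with a value already high.
   - From the entry limit to the >8x threshold: 8 / 2.5 = 3.2-fold.
   - From 2x to 9x ULN: 9 / 2 = 4.5-fold.
   - Both are high at baseline and high afterwards, so neither is a shift to high.

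3. **Which values each output uses.** For shift tables and listings, SAP 6.1 says "All visit assessment data will be included in shift tables and will appear in the subject listings". Other summary tables take one selected record per visit, and SAP 6.4 says "Analysis visit windows will be used for all lab, vital sign, and ECG data", choosing the record closest to the planned day. A peak at an unscheduled retest, such as the repeat within 48 to 72 h in protocol 6.10.9, can therefore be missing from the by-visit maximum.

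4. **Descriptive statistics (SAP 9.4).** The maximum by arm and visit can show that an extreme value occurred. It gives no count of subjects, no multiple of ULN (values are in SI units) and no pairing of ALT/AST with bilirubin.

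5. **Special-interest AE count (SAP 9.3.3, 9.3.3.1).** It is based on preferred terms. Because >3x ULN alone is already a laboratory AE (protocol 6.10.2), the category may mix such entries with protocol-defined hepatotoxicity, depending on the term list.

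6. **Discontinuation and severity tables (SAP 9.3.2).** Protocol 6.10.9 stops the drug for a confirmed or worsening >3x elevation as well as for hepatotoxicity, so stopping does not isolate the criteria. Severity is graded by effect on daily activity (protocol 6.10.1), not by laboratory level.

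Result: by-arm outputs that count subjects with ALT/AST >8x ULN, 0; by-arm outputs that count subjects with ALT/AST >3x ULN together with total bilirubin >2x ULN, 0.

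**Whether the data exist.** Protocol Appendix 2 schedules chemistry after baseline at weeks 12, 24, 36 and 48, then every 24 weeks, then at end of treatment and follow-up.
   - 104 weeks: 12, 24, 36, 48, 72, 96, plus 2 = 8 draws; 8 x 1650 = 13,200.
   - 156 weeks: adds 120 and 144 = 10 draws; 10 x 1650 = 16,500.

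These are upper bounds before withdrawals. They show that the table needs no new collection; they do not measure impact.

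**The case against.** The strongest reply is that these cases already appear by arm. Every subject meeting a criterion must be entered as a hepatotoxicity AE and stopped for good, so the case belongs in the special-interest table, its category listing and the table of TEAEs leading to treatment discontinuation. That includes the subject who goes from 2x to 9x ULN. This stands. A reader might infer that liver cases would be lost or go unreported by arm, and the documents do not support that.

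A reader might also infer that the shift tables leave out liver tests, or drop unscheduled values. Neither is supported. Protocol 9.6.4 covers each continuous parameter, the SAP does not say which parameters it selects, and SAP 6.1 puts all visit data into shift tables. A full baseline-by-post-baseline layout would also show high-to-high cells, though without the multiple. The table shells, the preferred-term list, the DSMB charter and the DSMB SAP are not among the documents and may add detail.

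Two further points are fair. The protocol never promises a ULN-multiple table, so the two documents do not contradict each other. And because 6.10.9 fixes the thresholds, the table could be made at reporting with little room for data-driven choice.

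What remains is that the by-arm AE figure depends on entry and coding, and no planned output tests it against the laboratory values. The SAP does use measured values elsewhere: glucose limits for hypoglycemia categories (9.3.3.2), biochemical findings in the DKA case definitions (9.3.3.5), and a macroalbuminuria cut-off for UACR (9.4).

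**Conclusion.** The point holds in a limited form. In the protocol and SAP text, no by-arm output counts subjects meeting the >8x ULN or the joint ALT/AST and bilirubin criterion, none checks the hepatotoxicity AE count against the laboratory data, and the shift-to-high count omits subjects already above ULN at baseline.

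The size is small. Qualifying cases should still be visible by arm through mandatory AE entry and stopping, and the primary HbA1c endpoint is untouched. The documents give no hepatic event rate, so the number of subjects concerned cannot be stated. The conclusion assumes that the unseen table shells do not already contain such a table. It is a minor improvement to safety reporting, worth making because it costs so little.

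**What to change.** Add one by-arm table (n, %) to SAP 9.4 for the Safety Analysis Set. Use all post-baseline laboratory values in the database, scheduled and unscheduled, and state that the one-record-per-window rule of SAP 6.4 does not apply. Count subjects with:

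- maximum ALT or AST >3x ULN, and >8x ULN;
- total bilirubin >2x ULN;
- ALT or AST >3x ULN with total bilirubin >2x ULN, shown twice: on the same sample date, and at any post-baseline times. Protocol 6.10.9 sets no timing, so same-date pairing alone would be stricter than the protocol.

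Footnote any counted subject whose baseline bilirubin was above 1.5x ULN, which entry permits for isolated Gilbert's syndrome. Keep the preferred-term count alongside, because the table does not cover the INR and symptom criteria, or local retests that are not in the database.

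The cost is a few lines of SAP text and one table, with no new procedure or staff. The downside is that its counts may differ from the hepatotoxicity AE count, so the report needs a short reconciliation note.

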4.3. SAFETY ENDPOINTS

The key safety endpoints include:

- A 5-point composite endpoint of CV death, non-fatal myocardial infarction, non-fatal stroke, hospitalization for unstable angina, or coronary revascularization
- A 6-point composite endpoint of CV death, non-fatal myocardial infarction, non-fatal stroke, hospitalization for unstable angina, coronary revascularization or hospitalization for heart failure
- Individual events including all-cause mortality, CV death, fatal and non-fatal myocardial infarction, fatal and non-fatal stroke, hospitalization for unstable angina, hospitalization for CHF, or coronary revascularization. Both first events and total events, taking account of repeat events will be examined
- Change in eGFR from baseline
- Change in UACR from baseline
- Incidence of adverse events of interest. Adverse events of interest including urinary tract infections (UTI), pyelonephritis urosepsis, genital mycotic infections (GMI), diuretic effects including hypovolemia, hypotension episodes, hypoglycemia, hepatotoxicity, fractures, malignancies, hypersensitivity reactions, acid-base disorders including diabetic ketoacidosis, rash, renal failure events, and amputations

Other safety endpoints include:

- Adverse events
- Clinical laboratory events
- Physical examinations
- Vital signs including orthostatic blood pressure
- Use of concomitant medications

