9. SAFETY

The safety endpoint of the program-wide meta-analysis is the hazard ratio for the time to first occurrence of adjusted MACE+. The analysis of this endpoint will not be discussed in this SAP.

The other safety endpoints include:

- Time to a 5-point composite adjudicated endpoint of CV death, non-fatal myocardial infarction, non-fatal stroke, hospitalization for unstable angina, or coronary revascularization
- Time to a 6-point composite adjudicated endpoint of CV death, non-fatal myocardial infarction, non-fatal stroke, hospitalization for unstable angina, hospitalization for heart failure, and coronary revascularization; and time to onset of event
- Time to individual events including all-cause mortality, CV death, non-fatal MI, non-fatal stroke, transient ischemic attack, hospitalization for unstable angina, hospitalization for heart failure, and coronary revascularization; and time to onset of each event
- Incidence of treatment emergent AEs (TEAEs) of interest
- Incidence of amputations
- Change from baseline in eGFR by study visit
- Change from baseline in UACR by study visit

Note that analysis for time to event endpoints (ie, first 3 bullets as listed above) will be included in a meta analysis plan, and not be included in this SAP.

Additional safety endpoints will also include:

- Incidence of all TEAEs
- Change from baseline as well as shift in clinical laboratory findings
- Change from baseline in vital signs measurements including orthostatic blood pressure
- Incidence of abnormal physical examination findings by body system
- Incidence of concomitant medication use

The analysis population used for safety analyses will be the Safety Analysis Set.

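### SAP 9.4 specifies only within-arm UACR ratios at week 24: no bexagliflozin/placebo ratio with a confidence interval is named, and later visits have no model-based comparison

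*Combined protocol and SAP*

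**What the plan says.** SAP section 4.3 places "Change in UACR from baseline" among the key safety endpoints. SAP section 9 and protocol section 9.6.4 are more specific: "Change from baseline in UACR by study visit".

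SAP section 9.4 gives the analysis. The one inferential model is stated as: "Change in log transformed UACR from baseline to week 24 will be analyzed by ANCOVA model". Treatment is in that model, since the list of effects ends "insulin use or not, and treatment. The log transformed baseline values will be used as covariate". The outputs are then named. First, "LS means for each treatment will be estimated at week 24". Second, a ratio defined as "the ratio of the week 24 geometric mean and baseline geometric mean", reported per arm, "and the corresponding two sided 95% CI by treatment arm will be calculated as the antilog of the LS mean" and of its confidence limits. The analysis is repeated in subjects with baseline macroalbuminuria (UACR above 300 mg/g), and section 9.4 later asks for the UACR analysis table in the insulin and sulfonylurea subsets as well.

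For visits other than week 24 the section provides summaries: geometric mean, geometric CV, quartiles, minimum and "maximum of UACR values will be presented at screening, baseline, and all post-baseline scheduled visits", overall and in the macroalbuminuria subset. A general laboratory rule in the same section adds change from baseline over time by arm.

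**The concern.** The randomized question about albuminuria is how the two arms compare. The named outputs compare each arm with its own baseline instead. A within-arm change combines any drug effect with whatever else shifts UACR between baseline and week 24. In the macroalbuminuria subset, which is selected on a high baseline value, both arms could fall through regression to the mean alone. The baseline covariate protects the between-arm contrast from this; it does not remove the shared shift from each arm's own ratio. The plan therefore names the more vulnerable quantity and leaves out the protected one.

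This also sets UACR apart from the SAP's efficacy models. Those for HbA1c, FPG, weight and SBP name an LS mean difference, the logistic models an odds ratio and the Cox models a hazard ratio. For the other renal endpoint, eGFR, protocol section 9.6.4 names LS mean treatment differences with 95% CIs. What is at stake is whether the report contains a randomized UACR comparison with its uncertainty.

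**Working it through.** The documents give no effect size, SD or power for UACR, so there is no planned figure to reproduce.

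**1. Modelled against scheduled visits.** SAP 9.4 has UACR drawn at weeks 24, 36 and 48, then every 24 weeks, and at end of treatment. The schedule footnotes give a total treatment period of 104 to 156 weeks.
- By week 104: weeks 24, 36, 48, 72, 96 = 5 visits, plus end of treatment = 6.
- By week 156: add weeks 120 and 144 = 7 visits, plus end of treatment = 8.
- Modelled: week 24 only, so 1 of 6 to 8. The laboratory schedule footnote says every 24 weeks, which would drop week 36 and give 1 of 5 to 7.

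**2. What can be recovered from the named outputs.** Write L_b and L_p for the bexagliflozin and placebo LS means of log UACR change. Both are adjusted to the same baseline, so

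exp(L_b − L_p) = exp(L_b) / exp(L_p).

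The between-arm point estimate is the quotient of the two reported ratios; for example, 85% / 100% = 0.85. Its variance is Var(L_b) + Var(L_p) − 2Cov(L_b, L_p). The covariance is not a named output, so the exact interval cannot be rebuilt from the table.

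**3. What the direct contrast would give (illustrative).** Arm sizes of 1100 and 550 come from SAP 3.7. The SD of log UACR change is assumed to be 0.8 to 1.2.

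SE = SD × √(1/1100 + 1/550) = SD × 0.0522

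| Assumed SD | SE of log ratio | CI factor exp(1.96 × SE) |
|---|---|---|
| 0.8 | 0.0418 | 1.085 |
| 1.0 | 0.0522 | 1.108 |
| 1.2 | 0.0627 | 1.131 |

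With 80% evaluable (880 and 440) the factor runs from 1.096 to 1.147. A ratio of 0.85 at SD 1.0 with all subjects evaluable would carry a 95% CI of 0.85/1.108 to 0.85 × 1.108, that is 0.77 to 0.94. The documents do not give the size of the macroalbuminuria subset, so nothing is computed for it.

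**4. What is lost if the arm intervals are compared by eye.** With equal SDs and LS means treated as independent, non-overlap of two 95% intervals requires a log difference above 1.96 × SD × (1/√1100 + 1/√550). The direct contrast requires 1.96 × SD × √(1/1100 + 1/550). The SD cancels:

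(0.03015 + 0.04264) / 0.05222 = 1.39.

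This corresponds to a two-sided level of 2 × [1 − Φ(1.96 × 1.39)] ≈ 0.006 instead of 0.05.

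**The case against.** There is a good case that this is a small matter, and most of it stands.

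- **Later visits are not ignored.** A reader might infer that UACR after week 24 is never estimated. The documents do not support that: geometric means are tabulated at every scheduled post-baseline visit, overall and in the macroalbuminuria subset. Neither document says that the by-visit endpoint must be model-based, so summaries can meet the wording.
- **The contrast exists in the model.** A reader might also infer that the between-arm effect is never estimated. Treatment is a fixed effect, so the effect is a parameter of the fit, and its point value follows from the two arm ratios. Placebo is reported alongside, so shared drift is visible. What is missing is a commitment to report the contrast with its interval. The table shells that the SAP refers to are not in these documents and may already show it.
- **The SAP departs from no protocol model.** Protocol 9.6.4 names a model for eGFR and none for UACR.
- **Week 24 is a reasonable time point.** It is the first post-baseline UACR draw. Under protocol 5.2.5 changes to glucose-lowering therapy are at the investigator's discretion afterwards, so later contrasts would carry more change in background treatment. A repeated-measures model is therefore an option and not a requirement.
- **The overlap comparison is not the SAP's rule.** The 1.39 factor describes a reader's shortcut. It does not show that any particular effect would be missed.

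None of this supplies the missing output: the SAP text names no between-arm UACR ratio with a confidence interval, at week 24 or at any other visit.

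**Conclusion.** The point holds as a gap in the specified output. The model is sound and already contains the answer, but only the within-arm ratios and their intervals are called for. Followed literally, the plan would report no randomized UACR comparison with a confidence interval, and visits after week 24 would have descriptive summaries only without the SAP saying that this is intended.

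The size is modest. The visit counts, and the conclusion that the point estimate but not the exact interval is recoverable, rest on the documents alone. The 1.39 factor assumes equal SDs and independent LS means. The interval widths rest on assumed SDs and are only illustrative. UACR is a safety endpoint outside the primary and key secondary testing sequence, and nothing here touches those conclusions, the sample size or the conduct of the trial.

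**What to change.** In SAP 9.4, add to the outputs of the existing ANCOVA the bexagliflozin/placebo ratio of adjusted geometric means at week 24, calculated as the antilog of the LS mean difference, with its two-sided 95% CI. Report it overall and in the macroalbuminuria, insulin and sulfonylurea subsets. The within-arm ratios can stay beside it.

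For the later scheduled UACR visits, choose one of two options:
- add a supportive MMRM on log UACR with treatment, visit, treatment-by-visit interaction, log baseline UACR and the same covariates, giving the between-arm ratio with its 95% CI at each visit; or
- state that visits after week 24 are descriptive only.

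The cost is SAP wording and one contrast from a model already planned, plus one supportive model if the MMRM option is chosen. No new data are needed.
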